17.2 Serious Breaches

The Medicines for Human Use (Clinical Trials) Regulations contain a requirement for the notification of "serious breaches" to the MHRA within 7 days of the sponsor becoming aware of the breach.

A serious breach is defined as "A breach of GCP or the trial protocol which is likely to affect to a significant degree:

- the safety or physical or mental integrity of the subjects of the trial, or
- the scientific value of the trial".

If a serious breach is suspected the sponsor must be contacted within 1 working day. In collaboration with the principal investigator, the serious breach will be reviewed by the sponsor and, if appropriate, the sponsor will report it to the REC committee, Regulatory Authority and the NHS host organisation within 7 calendar days.

17.3 Premature Subject Withdrawal

Subjects have the right to withdraw from the study at any time for any reason, without the need to justify. The investigator also has the right to withdraw subjects in case of AEs, protocol violations or administrative reasons. Please refer to section 8.9 for details.

Since an excessive rate of withdrawal can render the study inconclusively, the unnecessary withdrawal of subjects must be avoided.

18. FINANCE AND INSURANCE

18.1 Contractual and Financial Details

The investigator, the sponsor and CRO will sign a clinical study agreement prior to the start of the study outlining overall sponsor and investigator responsibilities in relation to the study. The contract will describe costs for pharmacy, laboratory and other protocol-required services.

Financial Disclosure Statements will be completed, as required by 21 CFR part 54.

18.2 Insurance

All subjects participating in this clinical study will be insured through Themis Biosciences GmbH. The Insurance will be contracted by the assigned CRO.

19. REPORTING AND PUBLICATION

19.1 Clinical Study Report

After all subjects terminated their study participation (either by completion of Visit 7 (day 365) or prematurely by early termination or are confirmed as lost to follow up), a clinical study report will be prepared by the sponsor or delegate in accordance with relevant guidelines.

19.1 Publication Policy

All results generated in this study will be considered to be strictly confidential. The investigators may not submit the results for publication or presentation without prior written permission of the sponsor. Authorship for any publication will be determined in mutual agreement.

1. OVERVIEW

1.1 Study Design

MV-CHIK-205 is a prospective, interventional, observer blinded, block-randomized phase II trial, comparing different dose levels of MV-CHIK in three different formulations ((lyophilized, liquid frozen and liquid Stabilizing and Protecting Solutions (SPS®)) to evaluate immunogenicity, safety and tolerability of this novel Chikungunya vaccine in 60 healthy volunteer female and male subjects. Placebo (physiological saline solution) will be applied to blind two different treatment schedules, evaluating single shot versus double shot treatment. The study will be conducted as a single study site.

After completion of screening procedures, subjects will be randomized to one of five treatment groups (A, B, C, D or E) and will receive injections according to the scheme outlined in the study flow chart (see [Section 1.5](#)).

Group A: 12 subjects will receive two low dose treatments with MV-CHIK 5×10^4 (± 0.5 log) TCID50 /dose on day 0 and 28 (lyophilized formulation).

Group B: 12 subjects will receive two low dose treatments with MV-CHIK 1×10^5 (± 0.5 log) TCID50 /dose on day 0 and 28 (liquid frozen formulation).

Group C: 12 subjects will receive two low dose treatments with MV-CHIK 1×10^5 (± 0.5 log) TCID50 /dose on day 0 and 28 (liquid SPS® formulation).

Group D: 12 subjects will receive two high dose treatments with MV-CHIK 1×10^6 (± 0.5 log) TCID50 /dose on day 0 and 28 (liquid frozen formulation).

Group E: 12 subjects will receive one high dose treatment with MV-CHIK 1×10^6 (± 0.5 log) TCID50 /dose on day 0 (liquid frozen formulation) and placebo on day 28.

Subjects will be observed for safety and immunogenicity for 56 days during the treatment period, starting with the first MV-CHIK vaccination at day 0 (Visit 1), day 14 (Visit 2), day 28 (Visit 3), day 42 (Visit 4) and day 56 (Visit 5). After this treatment period subjects will return to site at day 182 (Visit 6) and at day 365 (Visit 7) for collection of serum to follow up the durability of specific antibodies against Chikungunya. Serum samples for passive transfer will be collected on days 0, 28, 56 and 365.

Study duration per subject will be 12 months, comprising of 8 weeks treatment period from study day 0 (Visit 1) until day 56 (Visit 5) and 44 weeks follow up period, including Visit 6 and Visit 7 (post day 56 until day 365). Study subjects are free to participate in other clinical studies after completion of the treatment period on day 56. The end of study will be defined as date of the last visit of the last subject.

1.2 Study Objectives

1.2.1 Primary Objective

- To investigate immunogenicity and safety of MV-CHIK in different dose regimens, 28 days after one or two vaccinations

The immunogenicity will be determined by means of Plaque Reduction Neutralization Test 50 % (PRNT₅₀) 28 days after a single shot treatment at Visit 3 (study day 28) and 28 days after two treatments with MV-CHIK at Visit 5 (study day 56). Local and systemic AEs will be recorded and assessed.

1.2.2 Secondary Objectives

- To compare immunogenicity, safety and tolerability between different doses and formulations of MV-CHIK during the treatment period up to day 56
- To investigate the immunogenicity and safety of a novel liquid vaccine formulation
- To evaluate cellular responses induced by one or two immunizations
- To evaluate the long-term immunogenicity of MV-CHIK up to one year after the first MV-CHIK treatment
- To collect human sera for future efficacy evaluation, by passive transfer of anti-Chikungunya antibodies to virus susceptible non-human primates

1.3 Endpoints

1.3.1 Primary Endpoint

- Immunogenicity 28 days after the last MV-CHIK vaccination confirmed by the presence of functional antibodies as determined by the plaque reduction neutralization test (PRNT₅₀)

1.3.2 Secondary Endpoints

- Rate of solicited and unsolicited adverse events (AEs) during the treatment period until day 56
- Serious adverse events during the treatment period until study day 56
- Immunogenicity on days 0, 28 (group A, B, C, and D), days 0, 56 (group E) and long-term immunogenicity on day 182 (6 Month) and 365 (12 Month), confirmed by the presence of functional antibodies as determined by the plaque reduction neutralization test (PRNT₅₀).
- Measurement of anti-Chikungunya antibodies on days 0, 28, 56, 182 and 365 determined by enzyme linked immunosorbent assay (ELISA)
- Measurement of anti-Measles antibodies on days 0, 28, 56 determined by enzyme linked immunosorbent assay (ELISA)

Adapted from:

STAT03_A Statistical Analysis Plan

Version 6.0, Effective Date 16-Feb-2018

Confidential and intellectual property of Assign DMB. No part of this document or its contents may be duplicated, referenced, published or otherwise disclosed in any form or by any means without prior written consent of Assign DMB.

Page 7 of 29

[figure not shown]
06CJDX

- Induction of Chikungunya specific immune responses on days 0, 14, 28, 42 and 56 determined by T-cell assay.
- Safety laboratory parameters (hematology, serum chemistry, coagulation, urinalysis)

1.4 Sample Size Calculation

A formal sample size calculation was not conducted. The sample size of 60 subjects has been determined based on prior experience in evaluating the safety and immunogenicity of vaccines and is typical for early phase clinical studies. Sample size for this study was determined on grounds of feasibility and common practice in similar trials.

1.5 Flowchart

Adapted from:

STAT03_A Statistical Analysis Plan

Version 6.0, Effective Date 16-Feb-2018

Confidential and intellectual property of Assign DMB. No part of this document or its contents may be duplicated, referenced, published or otherwise disclosed in any form or by any means without prior written consent of Assign DMB.

Page 8 of 29

06CJDX

1.6 Schedule of Assessments

Visit	Screening	Treatment Period					Follow up Period		ET
		V1	V2	V3	V4	V5	V6	V7	
Study Day	-28 to -1	0	14 ±1	28 ±5	42 ±5	56 ±5	182 ±14	365 ±14	(7)
Informed Consent	X								
Inclusion/Exclusion Criteria	X	X							
Medical History	X	X							
Vaccination History	X								
Vital Signs (1)	X	X		X		X			X
Physical Examination (2)	X	X		X		X			X
Adverse Events (3)		X	X	X	X	X			X
Concomitant Medication(4)	X	X	X	X	X	X			X
Clinical Laboratory (5)	X			X		X			X
Pregnancy Test	X	X		X		X			X
Study Treatment (8)		X		X					
Dispense subject diary		X		X					
Collect subject diary			X		X				X
Local Tolerability (6)		X	X	X	X	X			X
Immunogenicity (PRNT ₅₀)		X		X		X	X	X	X
T-cell Immunity		X	X	X	X	X			X
CHIKV-antibodies (ELISA)		X		X		X	X	X	X
Measles-antibodies (ELISA)		X		X		X			X
Serum collection for passive transfer			X		X		X		X

(1) Assessment of vital signs will include systolic and diastolic blood pressure, pulse rate and body temperature
 (2) A full physical examination will be performed at screening and a system based physical examination will be done at Visit 1, 3 and 5, if necessary according to findings in a symptom-directed physical examination

(3) Conditions/symptoms noted prior to first IMP administration will be reported as medical history and not as AEs. At Visit 6 and 7 AEs will not be recorded as subjects are allowed to participate in other clinical studies during the follow-up period.

(4) Medications administered within 30 days prior to screening until end of treatment period will be documented as concomitant medication.

(5) Clinical Laboratory parameters include:

- Virology: HB s-Ag, anti-HB c-Ab, anti-HC-Ab, HIV-Ab (only once at screening)
- Hematology: hemoglobin, hematocrit, erythrocyte count, differential and total white blood count, platelets
- Chemistry: creatinine, potassium, sodium, calcium, AST, ALT, alkaline phosphatase, bilirubin
- Coagulation parameter: prothrombin time (PT), activated partial thromboplastin time (aPTT), fibrinogen
- Urinalysis: pH-value, glucose, protein, bilirubin, urobilinogen, blood, leucocytes esterase, nitrite, ketone and specific gravity. In case of abnormal findings, a microscopy will be done for confirmation.

Please refer to CSP section 8.11.1

(6) Local tolerability to be investigated 2 hours after each vaccination and additionally at the subsequent visits and prior to IMP administration.

(7) If the early termination occurs within the treatment period (at or before Visit 5), subjects shall perform all procedures as defined for Visit 5. If the early termination occurs within the follow up period (after Visit 5), subjects shall perform all procedures defined for Visit 7

(8) Administration of IMP will be performed according to allocated treatment group, after randomization at Visit 1

Adapted from:

STAT03_A Statistical Analysis Plan

Version 6.0, Effective Date 16-Feb-2018

Confidential and intellectual property of Assign DMB. No part of this document or its contents may be duplicated, referenced, published or otherwise disclosed in any form or by any means without prior written consent of Assign DMB.

Page 9 of 29

06CJDX

2. GENERAL CONSIDERATIONS

2.1 Conduct of Analysis

A preliminary analysis including safety and immunogenicity data will be performed after all subjects completed Visit 5 (day 56) and therefore terminated the treatment period of the study. The purpose of this analysis is to provide highly valuable data for further Chikungunya vaccine development including the efficacy evaluation, by passive transfer. Thus, immunogenicity analysis for PRNT₅₀ and ELISA results for chikungunya antibodies in the preliminary analysis will be performed for Visit 1 (day 0), Visit 3 (day 28), and Visit 5 (day 56). All safety analysis will be done in the preliminary analysis. Results from this preliminary analysis will not have any impact on the study design or the subjects during the follow up period of the study.

The final analysis will be conducted once the last subject has completed the study. All data of the study will already be available at the preliminary analysis except the immunogenicity data from Visit 6 and Visit 7, end of study data as well as other analyses requested from Visit 1 to Visit 5 for which no laboratory results are available at the time of the Day 56 analysis (T-cell analysis and ELISA results for measles). Thus only these data will be analyzed at the final analysis. If unexpected changes occur e.g. in the baseline or adverse event data, analyses may also be repeated at the final analysis.

2.2 Statistical Software and Quality Control

All statistical analyses will be performed using SAS® version 9.3 or higher. Tables, figures and data listings will be generated in Microsoft® Word® as well as PDF® format.

Quality control of SAS® programs will include a review of the whole process of result generation:

- Review of all analysis SAS® programs
- Review of SAS® log for errors, warnings and other notes that could indicate mistakes in the programs
- Review of all tables, listings and figures for completeness and correctness

2.3 Applicable Standard Operation Procedures

2.4 Blinding and Randomization

At Visit 1 (day 0) 60 eligible subjects will be randomly assigned to one of five treatment groups (A, B, C, D or E) by means of randomization envelopes provided by data management. All of these subjects will be equally distributed between the 5 groups using a randomization ratio of 1:1:1:1:1=A:B:C:D:E. A subject will be considered enrolled once the first IMP administration has been performed according to randomization.

As this study will be conducted in an observer-blinded manner, unblinded study team members responsible for randomization, preparation and administration of IMP, will otherwise not be involved in the conduct of the study. All subjects, the investigator and site personnel performing study related assessments, as well as the sponsor's representatives involved in the monitoring and conduct of the study, will be blinded to treatment assignment.

The primary endpoint as well as most of the secondary endpoints will be covered in the preliminary analysis after Day 56. The sponsor personnel and ADMB statisticians (blinded statistician) that perform and review the preliminary analysis will be unblinded at this point in time, but after the Blind Data Review Meeting ([Section 2.9](#)).

2.5 Descriptive Analyses

Descriptive analyses of continuous variables (summary statistics) will be described with the number of non-missing observations, arithmetic mean, standard deviation (\pm SD), median, quartiles (Q1 and Q3) and range (minimum and maximum).

Descriptive analysis of continuous immunogenicity variables (i.e. tables for the GMT and GMFI) will be described with the number of non-missing observations, geometric mean, confidence intervals for the geometric mean, standard deviation of logarithmic values, median, quartiles (Q1 and Q3) and range (minimum and maximum).

Categorical variables (frequency statistics) will be described with the number of non-missing observations and percentages (%). Percentages will be calculated within each stratum on the total number of non-missing observations, if not stated otherwise.

2.6 Inferential Analyses

The immunogenicity analysis will compare the functional anti-Chikungunya PRNT₅₀ antibody geometric mean titer (GMT) 28 days after the last MV-CHIK vaccination between the treatment groups. The significance level will be 0.05. All p-values will be two-sided and rounded to four decimal places.

GMTs and GMT ratios will be estimated by applying an analysis of variance (ANOVA) including the factor treatment group. This will be done using log10 transformed data and taking the anti-log of the resulting point estimates for the least squares means, least squares means differences and the corresponding 2-sided 95% Confidence Intervals (CI). P-values will also be provided to compare GMTs between treatment groups adjusted for multiple comparisons according to Tukey-Kramer.

Measles- and Chikungunya-ELISA titers as well as long-term stability of anti-Chikungunya antibodies determined by PRNT₅₀ and ELISA will be analyzed likewise.

Seroconversion rates will be compared between groups using a Fisher-Freeman-Halton test.

For the safety analysis Fisher exact tests will be provided for a comparison of AE rates between treatment groups.

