2.8 Handling Missing Data

Generally, missing values of immunogenicity variables will not be imputed, and the analysis will be limited to observed values. For missing data in AE evaluation concerning seriousness, severity or causality a worst case approach will be applied. In case of missing assignment to solicited or unsolicited, this AE will neither be counted in tables for solicited AEs nor in tables for unsolicited AEs but in tables for all AEs.

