1.2.3.1-1.2.3.6	n/a	Repeat tables 2.1.1-x2.1.6 for PP population (if not the same as Safety Population)	
Immunogenicity Results			
Primary Endpoint			
1.3.1.1	2.3.1.1	GMT of anti-Chikungunya PRNT ₅₀ Antibody 28 days after last MV-CHIK vaccination (mITT Population)	
1.3.1.2	2.3.1.2	ANOVA with fixed factor treatment group for GMT of anti-Chikungunya PRNT ₅₀ Antibody 28 days after last MV-CHIK vaccination (mITT Population)	
Anti-Chikungunya PRNT₅₀ Antibody			
1.3.1.3	2.3.1.3	GMT of anti-Chikungunya PRNT ₅₀ Antibody by Visit (mITT Population)	
 • Preliminary Analysis: Visit 1, 3 and 5 • Final Analysis : All available time points
1.3.1.4	2.3.1.4	ANOVA for GMT of anti-Chikungunya PRNT ₅₀ Antibody between treatment groups by Visit (mITT Population)	
 • Preliminary Analysis: Visit 1, 3 and 5 • Final Analysis : All available time points
1.3.1.5	2.3.1.5	Seroconversion rate for Anti-Chikungunya PRNT ₅₀ Antibody by Visit (mITT Population)	
 • Preliminary Analysis: Visit 1, 3 and 5 • Final Analysis : All available time points
Chikungunya-ELISA Antibodies			
1.3.1.6	2.3.1.6	GMT of Chikungunya-ELISA Antibodies 28 days after last MV-CHIK vaccination (mITT Population)	
1.3.1.7	2.3.1.7	ANOVA for GMT of Chikungunya-ELISA Antibodies between treatment groups 28 days after last MV-CHIK vaccination (mITT Population)	
n/a	2.3.1.8	GMT of Chikungunya-ELISA Antibodies by Visit (mITT Population)	
 • All available time points
n/a	2.3.1.9	ANOVA for GMT of Chikungunya-ELISA Antibodies between treatment groups by Visit (mITT Population)	
 • All available time points
n/a	2.3.1.10	Seroconversion rate of Chikungunya-ELISA Antibodies by Visit (mITT Population)	
 • All available time points
Measles-ELISA antibodies			
n/a	2.3.1.11	GMT of Measles-ELISA Antibodies 28 days after last MV-CHIK vaccination (mITT Population)	
 • All available time points

Adapted from:

Page 21 of 29

STAT03_A Statistical Analysis Plan

Version 6.0, Effective Date 16-Feb-2018

Confidential and intellectual property of Assign DMB. No part of this document or its contents may be duplicated, referenced, published or otherwise disclosed in any form or by any means without prior written consent of Assign DMB.

06CJDX

1.3.1.1 - 1.3.1.7	1.3.2.1 - 1.3.2.11	Repeat tables for PP Population	

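### Long-term antibody stability is analysed only as between-group titre differences at each visit; no fold decline, confidence interval for decline, or comparison of decline is specified

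*Combined protocol and SAP*

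**What the plan says.** A secondary objective in SAP 1.2.2 is: "To evaluate the long-term immunogenicity of MV-CHIK up to one year after the first MV-CHIK treatment". Protocol 4.5 presents antibody stability at 6 months and 1 year as something the design will show for the first time.

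For inference, SAP 2.6 says that GMTs and their ratios "will be estimated by applying an analysis of variance (ANOVA) including the factor treatment group", with p-values "adjusted for multiple comparisons according to Tukey-Kramer". It then states that "Measles- and Chikungunya-ELISA titers as well as long-term stability of anti-Chikungunya antibodies determined by" PRNT50 and ELISA are treated in the same way. Protocol 12.2 agrees: stability at the two late visits is compared between the five groups.

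The SAP 7.1 table list follows this. It has GMT by visit, seroconversion by visit, and an ANOVA table whose title contains "Antibody between treatment groups by Visit (mITT Population". SAP 2.5 refers to "tables for the GMT and GMFI", but SAP 5.1 lists no fold-change variable, 5.2 gives no derivation or reference visit, and 7.1 has no such table.

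On missing data, SAP 2.8 says that "missing values of immunogenicity variables will not be imputed, and the analysis will be limited to observed values". SAP section 5 keeps early-termination samples out of the summary tables, and protocol 8.9.2 does not replace withdrawn subjects.

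**The concern.** Stability is a change over time within a person. The planned model has no visit term, no subject term and no earlier titre. The Day 365 contrast therefore mixes two things: how far apart the groups were at their reference visit, and how differently they waned. A group with a high peak and fast waning can match or exceed a group with a lower, flat curve, and the ANOVA cannot tell them apart.

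A secondary objective could thus be reported without the quantity its name suggests. Timing adds to this. Under SAP 2.4, sponsor personnel and statisticians are unblinded at the Day 56 analysis, and Visits 6 and 7 are analysed later. A durability measure added after that point would be chosen with group titres up to Day 56 already known.

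**Working it through.** **Inputs from the documents.** Five groups of 12 (SAP 1.1; 5 × 12 = 60, as stated). MV-CHIK on Days 0 and 28 in A-D, and on Day 0 only in E. PRNT50 and CHIKV ELISA on Days 0, 28, 56, 182 and 365 (SAP 1.3.2, 1.6). Two-sided 0.05 (SAP 2.6). SAP 1.4 reports no formal sample size calculation, so there is no power or precision figure to reproduce.

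**Assumptions.** SD of log10 titre 0.3 to 0.7 at each visit; within-subject correlation r 0.3 to 0.8. The documents give neither.

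**1. What the planned contrast measures.** On the log10 scale:

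Day 365 difference between groups = difference at the reference visit + difference in change.

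If all groups wane equally, the last term is zero and the Day 365 ratio merely repeats the earlier one. Hypothetical case: group X falls from 400 to 100 and group Y stays at 100. The Day 365 ratio is 100/100 = 1, although X fell 4-fold. More subjects would not change this.

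**2. What can be read from the planned tables.** With complete data, Day 365 GMT ÷ Day 56 GMT equals the geometric mean of the paired ratios, so a reader could compute a point estimate by hand. The tables give no interval for it. If some subjects miss Day 365, the two GMTs no longer come from the same people.

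**3. Precision of a paired estimate.** The 95% CI factor for a group's fold change is 10^h, with h = t(11) × SD × √(2(1−r)) / √12 and t(11) = 2.201.

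| SD | r = 0.3 | r = 0.5 | r = 0.7 | r = 0.8 |
|---|---|---|---|---|
| 0.3 | 1.68 | 1.55 | 1.40 | 1.32 |
| 0.5 | 2.38 | 2.08 | 1.76 | 1.59 |
| 0.7 | 3.36 | 2.78 | 2.21 | 1.91 |

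Treating the two visits as independent at SD 0.5: h = t(22) × 0.5 × √(2/12) = 0.423, a factor of 2.65.

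**4. Comparing the fall between groups.** For a by-visit GMT ratio at SD 0.5: h = t(55) × 0.5 × √(2/12) = 2.004 × 0.5 × 0.408 = 0.409, a factor of 2.56. With the Tukey-Kramer multiplier 2.820 it is 3.76. For a ratio of fold changes, h is multiplied by √(2(1−r)). That is 1 at r = 0.5, so the factors are the same. At r = 0.8 it is 0.632, giving 1.81 and 2.31. The between-group interval is therefore narrower only if r exceeds 0.5.

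**5. Nominal intervals.**

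| Ratio | A-D | E |
|---|---|---|
| Day 182 over 28 days after last MV-CHIK | 182 − 56 = 126 days | 182 − 28 = 154 days |
| Day 365 over 28 days after last MV-CHIK | 365 − 56 = 309 days | 365 − 28 = 337 days |
| Day 365 over Day 182 | 183 days | 183 days |

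E's first two intervals are 28 days longer. With an assumed half-life of 60 to 200 days, common to all groups, this alone shifts a D/E comparison by 2^(28/60) = 1.38 to 2^(28/200) = 1.10 in favour of two doses. The third ratio has equal length in every group, although it starts 154 days after the last dose in A-D and 182 days after it in E.

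**The case against.** The strongest reply is that the documents define durability as levels. Protocol 5.2 speaks of detecting antibodies at 6 months and 1 year, and SAP 1.3.2 refers to the presence of functional antibodies on those days. Seroconversion by visit, compared with a Fisher-Freeman-Halton test, answers that directly, and GMTs with confidence intervals at every visit make any decline visible. This stands for the endpoint as worded. It does not cover the separate stability analysis promised in protocol 12.2 and SAP 2.6, or explain why GMFI is named and then dropped.

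A reader might also infer that the effect of the second injection is not estimated at all. The documents do not support that. D and E receive the same product and dose on Day 0, then MV-CHIK or placebo on Day 28. Their randomised contrast at Visit 5 is in the by-visit ANOVA, and it separates the second dose from elapsed time, which an uncontrolled Day 56/Day 28 change does not. The primary objective (protocol 5.1, SAP 1.2.1) is likewise defined by levels at Visits 3 and 5. The gap is confined to A, B and C, which have no one-dose arm. E is not a like-for-like control for them: its dose differs from all three, and its formulation from A and C.

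Nor is the Day 365 comparison wrong because A-D are nominally 337 days and E 365 days past their last MV-CHIK dose. Counting from the first vaccination is declared and compares regimens from randomisation. It is a matter of interpretation.

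Finally, paired ratios are also limited to subjects who return, and the later visits are subsets of the same randomised subjects. That is correct: pairing makes the ratio internally consistent but does not remove selection by dropout.

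**Conclusion.** The point holds for durability. The only inference planned for long-term stability compares levels between groups on a day. It gives no interval for the fall and no test of whether the fall differs by group, and GMFI is mentioned without being specified. This conclusion rests on the form of the model and needs no assumption about variance.

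The size of the gain does rest on assumptions. At SD 0.5 log10 the within-group factor is 1.6 to 2.1 for r from 0.8 to 0.5, and it runs from 1.32 to 3.36 over the whole range shown. For between-group comparisons there is no gain in precision at r = 0.5; the benefit is that the right quantity is compared. No dropout rate is given, so the effect of differing subsets cannot be sized.

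The primary analysis is not affected. The documents state no planned conclusion about single- versus double-shot durability, so it would be wrong to say that one has been left unsupported.

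**What to change.** Before the Day 56 unblinding, add to SAP 5.1, 5.2 and 7.1, for PRNT50 and CHIKV ELISA, per-subject log10 ratios. Report them as geometric mean fold change with 95% CI by group, compared between groups with the same ANOVA and Tukey-Kramer adjustment:

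- (a) Day 182 and Day 365 over the titre 28 days after the last MV-CHIK vaccination (Day 56 in A-D, Day 28 in E). State the unequal intervals, 126/309 days in A-D and 154/337 days in E, or express the result as decline per 30 days, which assumes a constant rate on the log scale.
- (b) Day 365 over Day 182, nominally 183 days in every group.

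Either use these to define GMFI or delete the term from SAP 2.5. Tabulate days since the last MV-CHIK dose but do not adjust for it, because it is nearly collinear with regimen.

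Add Day 56/Day 28 ratios for all groups as a descriptive estimate of the second-dose increment, mainly for A-C. Keep D versus E at Day 56 as the one- versus two-dose estimate at the high dose. Keep the by-visit ANOVAs and the seroconversion tables.

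The cost is SAP text and a few tables, with no new visits, samples or subjects; protocol 12.6 allows added analyses. There are two drawbacks. Only subjects with both samples contribute, so show the number of pairs. And because SAP 5.2 sets values below the LLOQ to half of it, a ratio ending there is limited by that floor, so show how many such ratios each group has.
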